8.7. Sub-group Analyses

The wearable data sub-group will be used to assess the feasibility, suitability, and added value of incorporating wearable devices into the study to complement psychosocial and behavioural features already captured through smartphone sensors. We will evaluate the quality of the data collected by wearables by assessing missingness and participant adherence to device usage over time. Specifically, we will track the percentage of missing data for each sensor (e.g., heart rate, sleep data, physical activity data, etc.) and assess adherence based on the number of days participants wore the device. To quantify feasibility, we will calculate the frequency of wearable device usage and assess any potential barriers to consistent engagement, such as device malfunction or participant non-compliance.

Additionally, we will investigate whether wearable data can provide more granular insights into psychosocial and behavioural risk factors. By correlating specific wearable metrics with corresponding outcome measures, we aim to determine whether these data can supplement or replace outcome assessments through questionnaires. For example, we will assess the relationship between heart rate, steps taken, and physical activity levels by comparing wearable data with the physical activity outcomes measured by the Global Physical Activity Questionnaire (GPAQ) or the International Physical Activity Questionnaire (IPAQ) assessed in the iBeChange app within the Health habit assessment. Pearson correlation coefficients (for continuous, normally distributed variables) or Spearman's rank correlation (for non-normally distributed variables) and visual correlation plots will be used to evaluate the strength and direction of these relationships. In addition, we will use Bayesian models to account for potential confounders such as baseline physical activity levels and demographic characteristics. Machine learning approaches will also be

explored to assess the concurrent validity between participant-reported outcomes and wearable data.

Alongside these evaluations, we will test whether participants using wearables demonstrate a higher degree of behavioural change compared to those who did not receive the devices. To assess this, we will compare smoking, alcohol, nutrition, physical activity, and psychosocial outcomes between the wearable and non- wearable groups. For these comparisons, we will use the same statistical methods described above, including Bayesian models and exploratory analysis techniques (e.g., t-tests for between-group comparisons). These analyses will help determine whether the use of wearables leads to more significant improvements in outcomes compared to conventional methods.

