and self-reported measures. To assess whether wearable data can improve the effectiveness of personalised recommendation s delivered by the recommender system in the intervention in future settings. To compare user's adherence and usability of the system between participants in the wearable substudy and those in the standard iBeChange group.	will also be registered Suitability evaluated via participant-reported satisfaction and perceived ease of use of wearables, measured through post-intervention questionnaires. Preliminary concurrent validity (correlation between wearable data with self-reported outcome measures in domains such as physical activity and psychosocial health). Changes in primary and secondary outcomes between participants in the wearable sub-study and the standard iBeChange group to evaluate the preliminary impact of the use of wearables on the intervention. Changes in satisfaction and adherence rates between participants in the wearable on the intervention.	ease of use helps determine if wearables are suitable for complementing the monitoring of psychosocial and behavioural health. Validating the correlation between wearable data and self-reported measures is essential to confirm that wearables can assess psychosocial and behavioural constructs. Comparing changes between groups helps evaluate whether wearables, by providing objective and timely data, can enhance the personalisation and effectiveness of the iBeChange intervention. Analysing usability and adherence reveals whether the use of wearables increases participant engagement, positively impacting their involvement in the intervention.	medium activity time; sedentary MET minutes and sedentary time; inactivity alerts; active calories (calories burned during physical activity); total calories (total number of calories burned during the day) • Psychosocial health: • Sleep data: heart rate; heart rate variability; latency (time it takes to fall asleep from the moment the subject gets into bed); temperature deviation; restless period; average breath; efficiency (ratio of time actually spent sleeping to the total time spent in bed); sleep score; light, deep and REM sleep time; readiness score (body's recovery status and physical preparedness); startend bed time. • Stress Resilience: daytime stress (in terms of heart rate, heart rate variability, motion and temperature throughout the day). • Satisfaction and usability of smart ring use

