4.4. Effectiveness data collection

Effectiveness measurement time points will be at baseline and after 12 weeks.

Among secondary outcome measures to assess the iBeChange intervention effectiveness compared to the control group (described in Table 3), one main secondary measure has been selected per health habit or psychosocial measure according to those behaviours or symptoms with most evidence of cancer risk. These are the following:

- Smoking: Number of smoked cigarettes per day
- Body Weight: Body mass index calculation
- Alcohol: Weekly alcohol consumption
- Nutrition: Intake of processed food and red meat per week
- Physical activity: Minutes of moderate to vigorous physical activity per week
- Psychosocial: PSS-4 score for perceived stress.

4.4.1. iBeChange questionnaire on Cancer Nutritional factors

After a thorough literature review, there were some extensively used nutrition questionnaires assessing for adherence to the Mediterranean diet. However, this is not the scope of this pilot study: we aim to specifically assess the nutritional groups associated with increased or decreased risk of cancer. No validated scale assessing these specific constructs was found. Therefore, the iBeChange consortium is developing an iBeChange questionnaire on Cancer Nutritional factors. Questions will be selected and validated through experts' panels in an iterative manner. A paper-

format protocol detailing the development and validation of the scale will be attached to this pilot protocol submission for IRB approval.

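### Correlation can show whether ring data supplement the questionnaires, but cannot by itself show that they can replace them (Protocol Section 8.7; minor, exploratory aim)

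*Protocol*

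**What the plan says.** Section 8.7 of the protocol gives the purpose and the method in one sentence: "By correlating specific wearable metrics with corresponding outcome measures, we aim to determine whether these data can supplement or replace outcome assessments through questionnaires". It then names the statistics: "Pearson correlation coefficients (for continuous, normally distributed variables) or Spearman's rank correlation (for non-normally distributed variables) and visual correlation plots will be used". The task set for these statistics is "to evaluate the strength and direction of these relationships". The worked example sets heart rate and steps against the physical activity questionnaires.

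Two further methods follow. For the first, "we will use Bayesian models to account for potential confounders such as baseline physical activity levels and demographic characteristics". The second is machine learning, to be "explored to assess the concurrent validity between participant-reported outcomes and wearable data". Table 3 in Section 4.2 lists the matching endpoint under the tertiary/exploratory objectives as "Preliminary concurrent validity (correlation between wearable data with self-reported outcome measures in domains such as physical activity and psychosocial health"), so concurrent validity is itself defined as correlation.

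The protocol names no mean difference, limits of agreement, concordance or intraclass coefficient, calibration or prediction error for this aim. It also gives no acceptable difference and no correlation threshold.

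**The concern.** Two different questions share one statistic. Whether ring data *supplement* a questionnaire is a question of association, and correlation is a reasonable first summary. Whether they can *replace* it also depends on level and scale: does the ring read systematically higher or lower, and does the gap grow with activity? A correlation coefficient is blind to both.

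Level matters here because the main physical activity measure is in absolute units: "Physical activity: Minutes of moderate to vigorous physical activity per week". One purpose of the pilot, according to Section 11, is to judge how suitable the outcome measures are before the full RCT. A high coefficient reported under the present wording could be taken as support for interchangeability that was never examined.

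This is not a detail left for the SAP, because the protocol itself ties correlation to the replacement question.

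**Working it through.** **Sample size behind the analysis.** Section 6.3 gives 33% of the intervention group, and Section 8.2 gives 90 per group: 0.33 × 90 = 29.7, which reproduces the stated figure of about 30 ring users. The protocol gives no SD, bias or margin for this comparison, so all minute values below are assumptions.

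**Why the coefficients cannot see an offset.** For any constant a and any b > 0, corr(q, a + b·w) = corr(q, w), for Pearson and for Spearman. A ring reading exactly half the questionnaire value throughout would give a coefficient of 1.

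**Constant offset.** Let s1 and s2 be the two SDs and d the mean difference.
- Lin's concordance: CCC = 2·r·s1·s2 / (s1² + s2² + d²)
- 95% limits of agreement: d ± 1.96·√(s1² + s2² − 2·r·s1·s2)

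With s1 = s2 = 100 min/week and r = 0.9, the SD of the differences is √(20,000 − 18,000) = 44.7, so the half-width is 1.96 × 44.7 = 88.

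| Offset (min/week) | r | CCC | Limits of agreement |
|---|---|---|---|
| 0 | 0.90 | 18,000/20,000 = 0.90 | -88 to +88 |
| 50 | 0.90 | 18,000/22,500 = 0.80 | -38 to +138 |
| 100 | 0.90 | 18,000/30,000 = 0.60 | +12 to +188 |
| 150 | 0.90 | 18,000/42,500 = 0.42 | +62 to +238 |

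In 5,000 simulated samples of 30 with true r = 0.9 and an offset of 100, the mean Pearson coefficient was 0.90, the mean Spearman 0.87 and the mean CCC 0.58.

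**Proportional offset.** Assume questionnaire minutes with mean 250 and SD 100, and ring = 0.5 × questionnaire + noise of SD 25.
- Ring SD = √(50² + 25²) = 55.9, so r = 50/55.9 = 0.89.
- Mean difference (ring minus questionnaire) = 125 − 250 = -125 min/week.
- SD of differences = √(50² + 25²) = 55.9, so the limits are -125 ± 109.6, about -235 to -15.
- Slope of difference on mean = (−0.375 × 10,000 + 0.5 × 625) / (0.5625 × 10,000 + 0.25 × 625) = −3,437.5/5,781.25 = −0.59. The gap widens with activity, so constant limits describe it poorly. A proportional-bias check is needed as well.

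**Which pairs can be tested for agreement.** Section 4.6 lists ring time and MET minutes by intensity level, and Section 4.4 has questionnaire minutes of moderate to vigorous activity. These share units if the ring's medium and high bands are taken as moderate and vigorous, which is an assumption. Heart rate, steps, heart rate variability and ring stress share no units with GPAQ or PSS-4. Table 2 has the ring delivered at Day 0 and GPAQ at baseline and Day 90 ± 7, so ring wear and GPAQ can overlap only at the end of the intervention.

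**Precision (a separate point).** At n = 30 the Fisher interval is 0.17 to 0.73 for r = 0.5, and 0.45 to 0.85 for r = 0.7. Limits of agreement are imprecise too: with SD of differences 44.7, each limit has a standard error of about 44.7 × √(3/30) = 14.1, or roughly ± 28 min/week.

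**The case against.** The strongest reply is that this turns on one word. *Replace* appears once, beside *supplement*. Elsewhere the protocol speaks of complementing questionnaire data: Section 3.1, the Table 3 objective, and the opening of Section 8.7 itself. The endpoint is exploratory and labelled preliminary, and correlation is an ordinary measure of concurrent validity. That limits the weight of the point but does not make the statistic fit the replacement question.

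A reader might infer that the pilot will use r to decide to swap the RCT's GPAQ outcome for ring minutes. The documents do not support this. Section 8.7 sets no threshold or decision rule, and Section 8.8 lists effect size, variability and sample size as what passes to the RCT, not a change of instrument.

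A reader might also infer that replacement requires identical values from both measures. That is too strict for an outcome compared between arms. An offset common to both arms cancels in the difference, and a common scale factor leaves a standardised effect unchanged. GPAQ is self-report and not a reference standard, so a bias against it does not show which measure is wrong. This stands, with one limit: rings go only to experimental participants (Table 5), so the pilot cannot check that an offset is common to both arms.

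The Bayesian models could in principle yield an intercept and slope. As described, however, they serve confounder adjustment, and machine learning serves concurrent validity, which Table 3 equates with correlation. The separate wearable deliverable (D5.2) may say more, but it is not at hand.

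Finally, limits of agreement cannot be computed for pairs without common units, which include the protocol's own examples of heart rate and steps. This is correct, and the fix must treat those pairs differently.

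**Conclusion.** The point holds in limited form. As written, Section 8.7 can answer *supplement* but cannot by itself answer *replace*, because its coefficients ignore constant and proportional offsets and no measure of bias or agreement accompanies them. This follows from the algebra and needs no assumed values.

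The illustrations (r near 0.9 with a mean difference of 100 or 125 min/week) show how far the two can diverge. They rest on assumed means, SDs and offsets and do not predict what the ring will show. The imprecision of r at about 30 users is a side remark and not part of the argument.

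The consequence is small: an exploratory conclusion could be overstated. No primary or secondary result, sample size or stopping rule of the pilot is affected.

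**What to change.** 1. **Pairs in common units** (ring moderate and high activity time, or MET-minutes, against GPAQ, over the same recall window at week 12): report the mean difference, a check for proportional bias (slope of difference on mean, or analysis on the log scale) and 95% limits of agreement, with confidence intervals. State that GPAQ is self-report and not a reference standard. Rest any statement on interchangeability on these results.
2. **Pairs without common units** (heart rate, steps, heart rate variability or ring stress against GPAQ or PSS-4): limit the conclusion to supplementing the questionnaire, and remove the replacement wording.
3. **All correlations**: report with 95% intervals.

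The cost is a short edit to Section 8.7 and a little more analysis of data already being collected. The drawback is that limits of agreement from about 30 ring users will be imprecise, so they should be presented as preliminary.

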Participants will also be asked for optional consent of voice recordings to analyse potential vocal stress markers. This will be registered and the option to record within the iBeChange app will only be displayed to those participants in the experimental group that have consented.

Regarding wearables, the ICF signature appointment and the introduction to the iBeChange app will also be used to deliver the device. The consumer-grade Oura ring has been selected. A stock of devices will be available at each recruitment centre. An Oura ring of the participant's size will be delivered and connected to the participant's iBeChange app account.

In case the needed size is not available at one centre, it will be requested at the other sites, and that participant will be excluded from the wearable sub-study so as not to delay the start of the intervention delivery.

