6.3. Experimental sub-group intervention: Wearable Sub-study (EGw)

Participants randomised to the experimental group will be offered the opportunity to join the wearable sub-sample until the required sample size is reached in each clinical centre. If participants agree, and after specific ICF signature, a second randomisation will take place to determine whether they are assigned to the wearable sub-sample or not. Participants assigned to the wearable sub-sample will be provided with an **Oura ring** of their size, and additional data will be collected from these participants.

A potential issue is that, despite purchasing ring sizes based on the most likely gender- and age-specific measurements of the recruited sample, there may still be instances where suitable sizes are not available for participants willing to join this subsample and assigned to the wearable sub-group. To address the potential unavailability of ring sizes for participants assigned to the wearable sub-group, several measures will be implemented. Firstly, the extra rings will be centrally stored at one clinical centre (i.e., IEO), enabling redistribution to other centres if needed. However, fingers other than the index finger may be used without compromising data collection. Furthermore, if a suitable ring size is unavailable for a participant, the enrolment can proceed with the next eligible participant included in the iBeChange intervention group if willing to and randomised to the wearable sub-group. Lastly, if one centre completes recruitment ahead of others, any surplus rings will be reallocated to centres still actively recruiting participants.

The study will provide clear instructions for device use, offer technical support if needed, and ensure participants are fully informed about data security measures by signing a specific informed consent form. In this pilot study, participants will be able to access the Oura ring app, where the visual progress tracking will be available. This can significantly enhance participant engagement and minimise the risk of non-adherence.

Participants will be enrolled across all three clinical centres involved in the pilot study (i.e., ICO, IEO, and UMFCD). 33% of the intervention group will receive a wearable device, corresponding to approximately 30 participants across all centres (180 participants is the total recruitment of the pilot study, 60 participants per centre).

[figure not shown]

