Based on the cancer screening type distribution observed in the pilot study, it is estimated that each clinical centre will have 10 participants with wearable devices, distributed as follows:

Table 8. Estimated recruitment per cancer screening type and clinical centre for the wearable sub-study

Cancer screening type	ICO	IEO	UMFCD
Breast (females)	7	8	7
Lung (males/females)	-	2	-
Colorectal (males/females)	3	-	3
TOTAL	10	10	10

If the ring is not available at the time of recruitment, the following workflow (**Figure 4**) will outline how the situation will be managed. The euro symbol means additional costs will be needed; the clock symbol means additional time, which results in the participants receiving the ring at a later stage.

Figure 4. Logistics workflow for wearable assignment depending on recruitment status and size availability

The intervention for participants assigned to the wearable sub-sample will be the same as in the experimental group, consisting of the behavioural change intervention through the iBeChange platform. Additionally, the Oura Ring will enable continuous and passive health monitoring, allowing accurate health assessments and, at future stages, potential support of the identification of risk factors and their targeting (adjusting the intervention if needed), and potentially encourage proactive behavioural changes by increasing participants' awareness of their health metrics.

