6.5. Measures to minimise bias: randomisation and blinding

Participants will be randomised into either the control or the iBeChange group, with stratification based on recruitment centre and cancer screening type.

For those in the iBeChange group, participation in the wearable sub-study will be optional. To prevent selection bias, participants who opt in will undergo a second randomisation to determine whether they receive the wearable device or not.

Due to the nature of the intervention—where only the experimental group receives a digital behavioural change program—blinding is not feasible in this pilot study. However, to minimise bias in outcome assessment, all evaluations will be conducted remotely, ensuring that responses from participants in both groups are collected without direct influence from healthcare professionals.

7. Data Flow, management and protection

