8.2. Sample size determination

The sample size for the pilot study was determined as 10% of the total sample for the full RCT, which covers its feasibility nature. For the full RCT, assuming a 60% refusal rate, a significance level of 0.05, and a 5% difference between groups, a sample size of 900 participants per group would result in a power of 80%. Therefore, the estimated sample size for the pilot was 180 participants (90 per group).

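### The exploratory wearable comparison is worded by ring use or receipt rather than by the second randomisation, and ring-allocated participants without a fitting size are excluded after allocation

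*Protocol*

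**What the plan says.** **Second randomisation.** Section 6.5 states: "For those in the iBeChange group, participation in the wearable sub-study will be optional". To guard against selection bias, "participants who opt in will undergo a second randomisation to determine whether they receive the wearable device or not". Section 6.3 limits the offer: experimental-group participants "will be offered the opportunity to join the wearable sub-sample until the required sample size is reached in each clinical centre". Table 5 adds skin and allergy exclusions that apply only to the ring.

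**Numbers.** Section 8.2 gives 180 participants, 90 per group. Section 6.3 says that "33% of the intervention group will receive a wearable device, corresponding to approximately 30 participants across all centres". Table 8 puts 10 at each centre.

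**Ring size.** In Section 5.2 (common procedures) the ring is handed over after the second allocation, and only if the size is in stock. If it is not, "that participant will be excluded from the wearable sub-study so as not to delay the start of the intervention delivery". Section 6.3 then moves on to the next willing participant who is randomised to a ring. The text introducing Figure 4, also in Section 6.3, instead describes extra time, "which results in the participants receiving the ring at a later stage".

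**Analysis.** Section 8.7 will "test whether participants using wearables demonstrate a higher degree of behavioural change compared to those who did not receive the devices". It goes on to speak of wearable and non-wearable groups without defining them, and names Bayesian models and t-tests. Table 3 (Section 4.2) contrasts sub-study participants with the standard iBeChange group.

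**The concern.** Only one group is exchangeable with the participants allocated a ring: those who also opted in and were randomised to no ring. The wording in Section 8.7 and Table 3 is wider. Within the experimental group, people without a ring can be:

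- opt-ins randomised to no ring
- people who declined the sub-study
- people ineligible under Table 5
- people enrolled after their centre's quota was filled, who were never offered a ring
- possibly, ring-allocated people whose size was out of stock

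Decliners may differ from opt-ins in motivation, and later enrolees may differ in other ways. A contrast that includes them mixes any ring effect with those differences, which is the bias the second randomisation was added to prevent.

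The size rule is a separate problem. Exclusion and replacement happen after allocation and only in the ring arm. The people concerned either leave the comparison or move to the non-receivers, and both break the randomised allocation. Section 8.7 intends to conclude whether wearable use leads to better outcomes, and that causal reading needs the randomised contrast.

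**Working it through.** **1. The plan's own figure.** 180 / 2 = 90 in the experimental group; 0.33 × 90 = 29.7, about 30 rings; 30 / 3 = 10 per centre. This agrees with Section 6.3 and Table 8. With 30 rings given out, 90 − 30 = 60 experimental participants have none.

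**2. Who those without a ring are.** The protocol states neither the second ratio, nor the uptake, nor a no-fit rate, so all three are assumptions. Uptake here means the share of those offered who are eligible and consent. Every ring is taken to fit, and centres are pooled.

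- Rings given = offered × uptake × ring share; offers stop at 30 rings or 90 people.
- Declined = offered × (1 − uptake); never offered = 90 − offered.
- Share not randomised to no ring = (declined + never offered) / (90 − rings).

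Example, 1:1 at 80% uptake: offered = 30 / (0.8 × 0.5) = 75; declined = 75 × 0.2 = 15; never offered = 90 − 75 = 15; share = 30 / 60 = 50%.

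| Ratio | Uptake | Ring | Randomised to no ring | Declined | Never offered | All without ring | Share not randomised to no ring |
|---|---|---|---|---|---|---|---|
| 1:1 | 70% | 30 | 30 | 25.7 | 4.3 | 60 | 50% |
| 1:1 | 80% | 30 | 30 | 15 | 15 | 60 | 50% |
| 1:1 | 90% | 30 | 30 | 6.7 | 23.3 | 60 | 50% |
| 1:1 | 100% | 30 | 30 | 0 | 30 | 60 | 50% |
| 1:2 | 60% | 18 | 36 | 36 | 0 | 72 | 50% |
| 1:2 | 90% | 27 | 54 | 9 | 0 | 63 | 14% |
| 1:2 | 100% | 30 | 60 | 0 | 0 | 60 | 0% |

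At 1:1 the decliners are 25.7 / 60 = 43% of the comparator at 70% uptake, 25% at 80% and none at 100%; the rest were never offered a ring. At 1:2 with incomplete uptake, fewer than 30 rings are given out.

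**3. Possible bias (illustration).** Suppose decliners differ from opt-ins by an assumed 0.3 SD in behavioural change, and the never-offered resemble the opt-ins. The shift is then 0.3 × declined / all without ring. At 1:1 this is 0.3 × 25.7 / 60 = 0.13 SD at 70% uptake and 0.3 × 6.7 / 60 = 0.03 SD at 90%, with no ring effect at all.

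**4. Exclusion for size.** At an assumed 10% no-fit rate, delivering 30 rings takes 30 / 0.9 = 33.3 ring allocations. About 3 allocated people would be lost, all from the ring arm.

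**5. Price of the randomised contrast.** SE = SD × √(1/n1 + 1/n2); detectable difference at 80% power and two-sided 5% = (1.96 + 0.84) × SE.

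- 30 v 60: √(1/30 + 1/60) = 0.224 SD; detectable 0.63 SD.
- 30 v 30 (1:1): √(1/30 + 1/30) = 0.258 SD; detectable 0.72 SD.
- Ratio of standard errors: 0.258 / 0.224 = 1.15, a rise of about 15%.

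**The case against.** **The authors may have meant the randomised contrast.** Other sections describe the second randomisation as deciding who does or does not receive a ring, so the phrase in Section 8.7 may echo that. The non-wearable group is undefined, and no sentence expressly puts decliners in it. This stands, and it limits the claim: the comparator is not restricted, rather than expressly non-randomised. Table 3's comparator is also undefined, but it is the looser wording and does not point to twice-randomised participants.

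**Other documents may settle it.** A separate deliverable (D5.2) covers the wearable component, and a statistical analysis plan may define the analysis sets. Neither is at hand. Either could add detail, but the wording here would still need correcting.

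**Confounders will be accounted for.** Section 8.5 says so, and Section 8.7 uses the same methods. Adjustment for measured variables does not remove selection on motivation.

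**Stock-outs are mitigated.** Section 6.3 provides for spare rings, redistribution and use of other fingers, and Table 3 records size shortages as a feasibility measure. This lowers the number affected but does not say how they are analysed.

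**The stakes are low.** The comparison is tertiary in a pilot that disclaims formal efficacy testing, and the illustrated shift of 0.03 to 0.13 SD is smaller than the standard error of 0.224 SD. This stands.

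**Conclusion.** The point holds for the wording and for the handling of size shortages. Followed literally, Section 8.7 and Table 3 give a contrast that is not protected by the second randomisation, and the size rule removes allocated people from one arm only. Under the assumptions shown, the part of the comparator not randomised to no ring is 50% at 1:1 and 14% to 50% at 1:2 with incomplete uptake. It is zero only at 1:2 with full uptake and every ring fitting.

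A reader might infer more than the documents support:

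- **That half of the comparator is self-selected.** The never-offered enrolled late and chose nothing. Decliners make up 0 to 43% at 1:1 for uptake of 100% down to 70%, and both ratio and uptake are assumed.
- **That finger size is linked to engagement or behaviour.** Section 6.3 ties ring size only to gender and age.
- **That Sections 5.2 and 6.3 flatly contradict each other.** Exclusion followed by moving to the next participant is coherent. The tension is only with the Figure 4 text, and that figure is not shown; late delivery may belong to one branch of its workflow.
- **That the control group is part of the comparator.** The words in Section 8.7 would allow it, but Table 3 points to the experimental group.

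The primary feasibility aims are untouched. What is affected is whether the exploratory result can be read as an effect of the ring.

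**What to change.** 1. In Section 8.7 and Table 3, define the comparison as ring versus no ring by second allocation, among participants who consented to the sub-study and were randomised twice. State the second allocation ratio.
2. Keep participants allocated a ring but without a fitting size in their allocated group for this comparison. Optionally, confirm that a fitting ring is available before the second randomisation, so that the situation rarely arises.
3. Describe decliners, those ineligible for a ring and those never offered one separately. Label any wider comparison as non-randomised.
4. Reconcile the exclusion wording in Section 5.2 with the later-delivery wording beside Figure 4 in Section 6.3.

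Items 1, 3 and 4 are changes of wording. The optional part of item 2 changes the order of steps at the visit and would have to be in place before enrolment. The statistical cost is a smaller comparator: at 1:1 about 30 instead of 60, with the loss of precision shown in the working. At 1:2 the cost is smaller. At 90% uptake it is 27 v 54 instead of 27 v 63, so the SE goes from √(1/27 + 1/63) = 0.230 to √(1/27 + 1/54) = 0.236 SD.
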